It is well known that interfascial plane blocks can result in systemic levels of LAs that achieve therapeutic concentrations (15) similar to that observed by intravenous infusions of LA (16,17). This is very likely the case for the ESP block, especially since the clinical and anatomical studies have conflicting findings regarding the loco-regional effects. Although intravenous lidocaine has shown some promise to prevent post-operative cognitive dysfunction (18,19), its effect on postoperative pain is not well studies. One study utilizing low dose lidocaine failed to show improvement in pain scores or opioid consumption, but the study did not utilize standardized multimodal analgesia

regimen (20). It is currently unknown whether the analgesic benefits of interfascial plane blocks are due to the multimodal analgesic regimen, the loco-regional benefits of the blocks, the systemic levels of local anesthetics following the block performance or a combination of all. We hypothesize that the mechanism by which the ESP block produces analgesia in the background of multimodal analgesia is probably related to the systemic absorption of local anesthetics. In addition, the safety of the ESP block using high doses of LA in cardiac surgery patients has not been rigorously assessed. We propose a pragmatic study to address both unknowns, the mechanism and safety of ESP following cardiac surgery.

III. Study Aims

- 1. The hypothesis of this study is that the analgesic effects of ESP can be attributed to its systemic distribution rather than its locoregional effects. A finding that lidocaine administered by ESP block achieves plasma concentrations in the analgesic range (2-5 ug/ml) at steady state will support our hypothesis whereas inability to reach analgesic levels will suggest that systemic distribution of local anesthetic is not a significant contributing factor of analgesia.
- 2. Despite the use of clinically acceptable doses, plasma concentrations of local anesthetic have been known to reach toxic levels following bilateral paravertebral blocks. This may also be true of ESP blocks. This study will address this concern and help establish a safety profile for ESP blocks in the cardiac patient population.

IV. Administrative Organization

University of Iowa Hospitals and Clinics—CVICU and Laboratories

V. Study Design

- i. Experimental design of the study (e.g., single-blind, double-blind): Randomized

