- ii. Study population general description: Adults undergoing elective cardiac surgery for coronary artery bypass graft (CABG) or valve surgery via sternotomy
- iii. Sample size determination and power analyses: 70 adult patients as determined using an online calculator available at: https://www.sealedenvelope.com/power/continuous-equivalence/
- iv. Study outcomes/endpoints:
 - 1. Arterial blood samples will be drawn and assessed for lidocaine concentrations
 - 2. Pain scores will be collected from EPIC electronic medical record or directly from the subjects.
 - 3. Opioid doses will be assessed and reported in morphine equivalents

VI. Study Procedures

- a. Subject selection procedures
 - i. Inclusion: Any patient >18 years and <81 years undergoing elective cardiac surgery for CABG or valve surgery via sternotomy and surgical procedure is not greater than 12 hours

Exclusion: Allergy to study medications; major livor or kidney dysfunction; BMI <20 or >50; revision surgery; Off-pump coronary artery bypass surgery; surgery via thoracotomy; narcotic dependent (opioid intake morphine equivalent > 10 mg/day for more than 3 months); other sources of chronic pain such as fibromyalgia; patients with associated significant central nervous system, liver, renal or respiratory disease; coexisting hematological disorder or deranged coagulation parameters; lack of informed consent; preoperative neurological deficits; and emergency surgery (E1, E2 and E3 classifications only).

ii. Recruitment procedures

- **1. Where will recruitment occur?** Pre-surgical clinic or Day of Surgery Admissions (DOSA)
- **2.** Where and when will consent be obtained? DOSA prior to surgery or in pre-surgical clinic
- 3. Who will obtain consent? Anesthesia team
- 4. What is the advertising plan, if applicable? N/A
- 5. What recruitment materials will be provided to the potential participant (brochures/information sheets/video presentation)? None.

iii. Screening procedures

- 1. What procedures are required for screening? Prior to the surgical procedure, the anesthesia team will review eligibility criteria: Allergic to study medication; diagnosed with major liver or kidney dysfunction; any bleeding disorders; in females verify non-pregnant state.
- 2. What is the screening schedule (number of visits, length of visits)? This will occur only on the day of surgery and will last approximately 30 minutes.

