- 3. Which screening tests/procedures are part of standard care and which are for research purposes only? All screening procedures listed above are part of standard of care.
- 4. What happens with screen failures (including any data gathered during screening)? A screening

log will be maintained and will be destroyed at upon study completion.

b. Randomization procedures (if applicable)

Participants will be randomized to IV or ESP groups using a computer-generated block randomization sequence and the allocation concealment will be ensured using a sealed envelope technique. The randomization sequence will be available with the PI and the research team.

c. Study Intervention

- iv. For Drug/device studies:
 - 1. Active study agents: Lidocaine
 - 2. Placebo study agents: None
 - **3. Blinding/labeling/preparation of agents:** Drug will be provided through the UIHC Investigational Drug Service
 - **4. Storage:** Room temperature. Protect from light.
 - **5. Administration:** Per study, either through ESP catheter or intravenously.
- 6. Toxicities and guidelines for adjustments: Acute emergencies from local anesthetics are generally related to high plasma levels encountered during therapeutic use of local anesthetics or to unintended subarachnoid injection of local anesthetic solution.

Management of Local Anesthetic Emergencies The first consideration is prevention best accomplished by careful and constant monitoring of cardiovascular and respiratory vital signs and the patient's state of consciousness after each local anesthetic injection. At the first sign of change, oxygen should be administered.

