 - Anxiolytic medications. Minimal anxiolytic medications given before surgery including midazolam given by anesthesia provider.
 - B. Intra-Operative Phase (Standard of Care At discretion of Anesthesia Provider)
 - Intraoperative opioid administration. Fentanyl IV given as needed for pain but typically < 1 mg for procedure.
 - Hydromorphone 0.5 1 mg given near completion of procedure
 - Intraoperative multimodal analgesia. If time since preoperative acetaminophen dose significantly exceeds 6 hours, acetaminophen 1000 mg IV, or via NG route is considered
 - Postoperative sedation initiated. Near the end of the procedure, dexmedetomidine or propofol infusion is begun for postoperative sedation in ICU while intubated

• All patients will receive dual post-operative nausea and vomiting (PONV) prophylaxis in the form of ondansetron and dexamethasone at appropriate time periods.

If the surgical procedure takes longer than 12 hours, the subject will be withdrawn from the study.

C. Block Performance/Procedure

• Upon arrival to the CV-ICU, patients will be assessed for eligibility to extubate based on hemodynamic and pulmonary stability on a case-by-case basis with the aim to extubate as early as possible. When appropriate, extubation will proceed following the CV-ICU Fast Track Extubation protocol that is already in place. Extubation is not required prior to the administration of study drug via IV or ESP catheters route. Participation in the study can proceed as long as after assessment by clinicians, the subject is extubated or ready to be extubated.

[figure not shown]
D. Group ESP (Study Procedures)

- Bilateral ultrasound guided erector spinae plane (ESP) catheters will be inserted either pre- or post-operatively.
- After confirming that there are no contra-indications, the subject will receive lidocaine via ESP catheter.
- Patients will receive lidocaine at a dose of 2 mg/kg ideal body weight (IBW) as bolus divided equally between the two ESP catheters.
- Subjects will then lie in a supine position.
- Lidocaine infusion via ESP catheters either through 2 dedicated pumps or via a single pump and a y-connector at a rate of 2 mg/kg/hour for approximately 48 hours.
- Blood samples will be drawn at 5, 30, 60, 120 minutes, 6 and 24 hours and assessed for lidocaine concentration.

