An adverse event or suspected adverse reaction is considered "serious" if, in the view of either the investigator or sponsor, it results in any of the following outcomes: Death, a life-threatening adverse event, inpatient hospitalization or prolongation of existing hospitalization, a persistent or significant incapacity or substantial disruption of the ability to conduct normal life functions, or a congenital anomaly/birth defect.

Any adverse experience that places the subject, in the view of the investigator, at immediate risk of death from the reaction as it occurred, or it is suspected that the use or continued use of the product would result in the patient's death.

ii. What procedures will be used to monitor subject safety?

Careful and constant monitoring of cardiovascular and respiratory (adequacy of ventilation) vital signs and the patient's state of consciousness should be accomplished. It should be kept in mind at such times that restlessness, anxiety, tinnitus, dizziness, blurred vision, tremors, depression or drowsiness may be early warning signs of central nervous system toxicity.

For the purpose of being prepared to deal with the side effects of lidocaine (Bradyarrhythmia, hypotension, infusion site reactions), the blocks will only be performed in the Cardiac ICU, where pharmacological and non-pharmacological measures are available to treat these side effects. The foundation of local anesthetic toxicity is outlined in seizure management with pharmacological seizure management, advanced cardiac life support (ACLS) to support the heart and use of 20% lipid emulsion to reverse local anesthetic toxicity. Oxygen can be provided for patients needing improved oxygenation and all the emergency medications, pharmacists and intensivists are readily available in the ICU.

- iii. Who (list names) will identify, document, and report adverse events? Nursing staff in the CVICU should report adverse events to [name] or [name] within 12 hours of the event. After the subject is stabilized this information will be reported to a member of Anesthesia Innovative Research Core who will report the event to the IRB.
- iv. What is the frequency for review of summarized safety information and who will perform the review (e.g., safety monitoring board)?

No committee is currently in place for this pilot study.

v. What are the stopping rules with regard to efficacy and safety?

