If an adverse/serious adverse event occurs, the study will be paused until careful evaluations is performed.

VIII. Analysis Plan

Study variables will be collected and tabulated. The continuous and discrete variables will be presented as mean and standard deviation after calculation and the categorical variables will be presented as frequencies. Normality of distribution will be assessed using Q-Q plots followed by Shapiro-Wilk test. Normally distributed data will be assessed using independent sample t-test and non-normally distributed data will be assessed using Mann-Whitney U-test. Categorical variables will be tested using chi-square tests or Fisher's exact test. Tests for equivalence will be applied for the primary outcome measures

failing which, tests of superiority will be applied. P values <0.05 will be considered statistically significant.

IX. Literature Cited

- 2. LahtinenP, Kokki H, Hynynen M. Pain after cardiacsurgery: A prospective cohort study of 1-year incidence and intensity. Anesthesiology. 2006;105 (4):794–800. doi:10.1097/00000542-200610000-00026
- 5. Reimer-Kent J. From theory to practice: preventing pain after cardiac surgery. Am J Crit Care. 2003;12(2):136–143.

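### Does the plan's silence on a patient's own infusion after an adverse event, and on data taken after an interruption, bias the trial toward equivalence?

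*Combined protocol and SAP*

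**What the plan says.** Section VII.v (stopping rules) is one sentence: "If an adverse/serious adverse event occurs, the study will be paused until careful evaluations is performed". It does not say whether the pause covers enrolment, new dosing or infusions already running.

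Section VI.c, item 6, opens: "Toxicities and guidelines for adjustments: Acute emergencies from local anesthetics are generally related to high plasma levels". That sentence goes on to name accidental subarachnoid injection as a second cause. The text that follows covers monitoring, oxygen, airway, convulsions and circulation, and does not mention the infusion. Section VI.d plans an infusion of about 48 hours in both arms, with blood samples at 5, 30, 60 and 120 minutes, 6 hours and 24 hours. The only patient-level withdrawal rule is: "If the surgical procedure takes longer than 12 hours, the subject will be withdrawn from the study". Section VII.iii has nursing staff report events "within 12 hours of the event". Section VII.iv says that no committee is in place.

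Aim 1 is supported if lidocaine given by ESP block "achieves plasma concentrations in the analgesic range (2-5 ug/ml) at steady state will support our hypothesis". Aim 2 rests on the statement that "plasma concentrations of local anesthetic have been known to reach toxic levels following bilateral paravertebral blocks". Section V.iv lists three outcomes: lidocaine concentration ("Arterial blood samples will be drawn and assessed for lidocaine concentrations"), pain scores and opioid dose. It names none as primary. Section VIII says: "Tests for equivalence will be applied for the primary outcome measures", with superiority as the fallback. It gives no margin and no rule for data recorded after an interruption.

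**The concern.** The trial measures plasma lidocaine, and toxicity is one reason an infusion might be stopped. If patients with the highest levels are the ones interrupted, their later samples are lowered or lost. The arm with truly higher levels then loses more, and the observed difference shrinks. In an equivalence trial a shrunken difference favours the claim. Aim 1 refers to steady state, and a sample drawn off infusion is not at steady state. Aim 2 looks for high levels, and those are the ones that would go missing. With no rule fixed in advance, the analyst could keep or drop such samples after seeing the data.

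**Working it through.** **Time scale.** With first-order decline, 5 × 2^(−x) = 2 gives x = log2(5/2) = 1.32 half-lives. For an assumed half-life of 1.5 to 4 h that is 2.0 to 5.3 h. The gap between the last two samples is 24 − 6 = 18 h. So an unrestarted interruption in that gap could move a 24 h level from the top of the stated analgesic range to the bottom. The mechanism is possible. On the other hand, five of the six samples are taken by 6 h and none after 24 h, so an interruption in the second half of the 48 h infusion touches no concentration.

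**What cannot be reproduced.** The plan's only figure is 70 patients. With n per arm = 2(SD/margin)²(z(1−α) + z(1−β/2))² and 35 per arm (1:1 assumed), the implied margin is 0.700 to 0.862 SD, for one-sided α of 0.05 or 0.025 and power of 80% or 90%. The documents do not let one choose, so every rate below rests on an assumed margin.

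**Plasma level, level-linked interruption.** Assumed inputs: 35 per arm; lognormal levels; medians 4 v 3 or 3.5 v 2.5 µg/ml; CV 30% or 40%; margin equal to the true mean difference (1.04 to 1.08 µg/ml); two one-sided Welch t-tests at 5%. A patient above 5 µg/ml is interrupted with probability q. The sample is drawn two half-lives later (0.25 of its value) with no restart.

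| q | Interrupted in higher arm (mean number) | False equivalence, used as drawn | False equivalence, excluded |
|---|---|---|---|
| 0 | 0 | 5-6% | 5-6% |
| 10% | 0.4-1.0 | 8-10% | about 7% |
| 30% | 1.2-3.0 | 15-24% | 10-11% |
| 50% | 2.0-4.9 | 27-47% | 14-19% |

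For Aim 2 (median 4, CV 40%) the true share above 5 µg/ml is P = 0.281. Used as drawn, the seen share is P(1−q) = 0.253, 0.197 and 0.141. Excluded, it is P(1−q)/(1−qP) = 0.260, 0.215 and 0.164. This treats each patient as having one sample. A high level already drawn before the interruption is not erased.

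**Same model, one assumption changed.**

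- 10% interrupted at random in both arms, samples excluded: 5-6%, the baseline.
- 10% interrupted at random in both arms, used as drawn: about 8-9%.
- 10% interrupted in the lower-level arm only, used as drawn: about 1%, which is away from equivalence.
- Level-linked, q = 10%, but the level is back to 75% when sampled: about 6-7%. With full recovery the effect is nil.

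**Pain.** Assumed: 35 per arm, margin 0.786 SD, interruption in 25% of the IV arm and 5% of the ESP arm, and pain 1 or 2 SD higher after interruption. The shift in the mean difference is (0.25 − 0.05) × 1 or 2 = 0.20 or 0.40 SD.

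| True state | P(equivalence), no effect of interruption | With rise of 1 SD | With rise of 2 SD |
|---|---|---|---|
| Arms equal | 0.89 | 0.73 | 0.37 |
| IV worse by the margin | 0.048 | 0.008 | 0.001 |
| IV better by the margin | 0.049 | 0.19 | 0.37 |

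Two rows move away from equivalence and one moves toward it.

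**Would a stricter rule help?** One candidate replaces an interrupted patient's lost values with the highest on-infusion value in that arm. If 10% of the lower-level arm is interrupted, this analysis by itself declares false equivalence in 21-22% of trials. If the arms are truly equal (median 3.5, CV 40%, margin 1.08) and 10% of one arm is interrupted, it cuts P(equivalence) from 0.81 to about 0.50. Restricting to on-infusion samples answers a different question from comparing arms as randomised, and which question is wanted is open to debate.

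**The case for a change.** The best case for acting is that the omissions are facts of the text and the situation is foreseeable. The adverse-event definition in VII.i is broad, the patients have just had open heart surgery, and the protocol itself links acute emergencies to high levels. A rule fixed before the data are seen would need no extra patients or blood samples, and choosing the handling afterwards leaves an equivalence claim open to challenge.

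Part of this stands. Both silences are real. For plasma level, interruption that tracks high levels does pull toward equivalence, whether samples are kept or dropped, when the higher-level arm is interrupted more.

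The rest does not carry. The link to level comes from a sentence about acute emergencies that also names a second cause, while VII.v is triggered by any adverse event, which VII.i defines without regard to cause. The 5 µg/ml cut-off in the simulation is the top of the analgesic range, and no section makes it a threshold for interruption. VII.v speaks of a pause until evaluation, which suggests resumption, whereas the large figures assume none. Aim 1's stated criterion is whether ESP levels reach a range, not the two-arm test that was simulated. The sections are silent rather than contradictory. The missing evaluator is weak evidence of a gap, since the recipients in VII.iii were removed from the public text, although that item assigns reporting only.

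**Conclusion.** No change to the plan follows. The plan leaves two things unsaid, but it states no rule that gives a wrong result. An interruption is a visible bedside event in an ICU. On the assumption that infusion times are charted there, an analyst can mark which samples were drawn off infusion, show results with and without them, and report interruptions by arm. That is ordinary handling for a short two-arm trial and does not depend on an amendment.

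The bias claim holds only in a conditional form: plasma outcome, level-linked interruption, more of it in the higher-level arm, and levels not recovered at sampling. Under those conditions and the assumed margin, false equivalence goes from 5-6% to 8-47% used as drawn, or 7-19% excluded. With interruption in the lower-level arm only it drops to about 1%, and with no interruption there is no effect. For pain the direction is undetermined, and the same reasoning applies to opioid dose. Interruption rate, threshold, half-life and margin are all assumed, so the documents support no particular size. The strict replacement rule would bring errors of its own. How an infusion is managed after an event is a clinical matter for the investigators, and nothing here bears on what that rule should be.

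### A normality pre-test chooses between the t-test and Mann-Whitney, its link to the equivalence test is not stated, and the quantity compared can change across the six concentration sampling times

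*Combined protocol and SAP*

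**What the plan says.** The title calls the trial an equivalence study. Section VIII (Analysis Plan) summarises continuous variables by mean and standard deviation, then gives a selection rule: "Normality of distribution will be assessed using Q-Q plots followed by Shapiro-Wilk test". It continues: "Normally distributed data will be assessed using independent sample t-test and non-normally distributed data will be assessed using Mann-Whitney U-test". The plan does not say what threshold applies, whether the check is made per arm or on pooled data, whether it is repeated at each time, or on what scale.

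A separate sentence follows: "Tests for equivalence will be applied for the primary outcome measures", with superiority tests if equivalence is not shown. The equivalence procedure, its scale, its interval and its margin are not given. The only level stated is "P values <0.05 will be considered statistically significant".

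Section V.iv lists three outcomes and labels none primary. The first is "Arterial blood samples will be drawn and assessed for lidocaine concentrations". The study procedures for both groups (section VI.d) place the samples at 5, 30, 60 and 120 minutes and at 6 and 24 hours. No summary exposure measure and no repeated-measures model is described.

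**The concern.** An equivalence conclusion needs one effect measure on one scale, with an interval to hold against a margin. Under the written rule, the observed shape of the data settles which quantity is compared. The t-test concerns a difference in means. Mann-Whitney concerns the ordering of the two distributions, and as written it delivers only a p-value.

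Positive concentration data are often right-skewed, and there are six times, so the rule can give a mean comparison at one time and a rank comparison at the next within the same trial. The reader could not line these up as one answer about the two routes. What is at stake is interpretability: a changing estimand and no interval.

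**Working it through.** **Inputs.** From the documents: 70 patients in total (section V.iii), two block-randomised arms (section VI.b), six sampling times, and significance at 0.05. Assumed, because the documents are silent: 1:1 allocation (35 per arm), log-normal concentrations, the CV, the within-patient correlation between times, a Shapiro-Wilk threshold of 0.05, and a switch to Mann-Whitney if either arm rejects.

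**The plan's own figure.** The basis given is "70 adult patients as determined using an online calculator available at" a continuous-equivalence web page, with no margin, SD or power, so 70 cannot be reproduced. Solving n per arm = 2(z(1-α) + z(1-β/2))² / (margin/SD)² backwards, a margin/SD of 0.70 with one-sided 0.05 and 80% power gives 2 × (1.645 + 1.282)² / 0.49 ≈ 35 per arm, or 70. Other settings fit too: about 0.79 (one-sided 0.05, 90% power), 0.78 (one-sided 0.025, 80%) or 0.86 (one-sided 0.025, 90%).

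**Step 1: how often the rule selects Mann-Whitney.** The log-scale SD is s = √ln(1 + CV²). If one arm rejects with probability p, either arm rejects with probability 1 - (1 - p)². At CV 30%, p = 0.412, so 1 - 0.588² = 0.65. Simulated rates (4,000 runs):

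| CV | Either arm rejects | Pooled 70 values reject |
|---|---|---|
| 15% | 27% | 26% |
| 20% | 39% | 39% |
| 25% | 53% | 56% |
| 30% | 65% | 71% |
| 40% | 85% | 90% |
| 50% | 94% | 97% |
| 60% | 98% | 99% |

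Repeat runs differ by about a point (40%, 65%, 84% and 93% at CV 20%, 30%, 40% and 50%). Pooling the arms does not change the picture.

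**Step 2: how often the six times do not all use the same test.** Either-arm rule, between-time correlation 0, 0.5 or 0.8 (1,500 runs):

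| CV | Mixed methods |
|---|---|
| 20% | 78-94% |
| 30% | 75-92% |
| 40% | 46-63% |
| 50% | 24-34% |
| 60% | 9-12% |
| 80% | about 1% |

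Repeat runs put the chance that all six times share one test at about 10-29% at CV 30% and 38-51% at CV 40%. Skewness is not needed for switching: with normal data and independent times, twelve checks at 0.05 give 1 - 0.95¹² = 0.46.

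**Step 3: what a Mann-Whitney p-value says about equivalence.** With a true ratio of 1.25, the test is non-significant in 14%, 34%, 52% and 64% of trials at CV 30%, 40%, 50% and 60%. Non-significance therefore cannot stand in for equivalence.

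**Step 4: the alternative.** Two one-sided tests on log concentration, equivalent to a 90% interval for the geometric mean ratio, declared equivalence falsely in at most about 5% of runs when the true ratio lay at the margin. Power with a true ratio of 1 and two illustrative margins:

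| CV | Margin 0.80-1.25 | Margin 0.667-1.5 |
|---|---|---|
| 30% | 86% | 100% |
| 40% | 56% | 99% |
| 50% | 24% | 95% |
| 60% | 5% | 84% |

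A 90% Hodges-Lehmann interval on the log scale covered the true shift in 90-91% of runs.

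**The case against.** The best defence is that section VIII contains two separate rules. The pre-test may govern only general comparisons and the superiority fallback, with the equivalence test to be specified elsewhere. That stands as far as it goes. A reader might infer that Mann-Whitney is the equivalence test, or that a non-significant result will be read as equivalence; the documents say neither. They leave the link open.

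Four other stronger readings are tempting and are not supported:

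- **That a rank analysis cannot use a margin.** It can, through a Hodges-Lehmann shift and interval. The plan simply specifies no interval, and the t-test branch has the same omission.
- **That most concentration data will go to Mann-Whitney.** Under the log-normal assumption this holds from a CV of about 25% upward, not at 20% or below. No CV is given, and the Q-Q plot step adds a judgement that the simulation does not model.
- **That concentration is the primary equivalence outcome.** No outcome is labelled primary, and the first aim in section III sets ESP concentrations against an analgesic range of 2-5 µg/ml, not against the other arm.
- **That error rates are seriously distorted.** The effect of the pre-test on test power is only 1-2 percentage points.

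The two problems also trade off. Switching is most frequent at a CV of about 20-30%; at high CVs nearly every time goes to the rank test and switching is rare.

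Finally, the missing margin is the larger gap. That is fair, but adding a margin alone would leave the choice of method to the data and the estimate undefined.

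**Conclusion.** The point holds in a limited form. The selection rule is written in advance, but it leaves the method, and so the quantity compared, to the observed data. Its relation to the equivalence tests is unstated, and no estimate, interval or scale is specified. Across six sampling times a mixture of methods is more likely than not at a CV of 20-30%, about an even chance at 40%, and uncommon from 60% upward. These sizes rest on the assumed log-normal shape, 35 per arm, 0.05 threshold and per-arm check. The absence of any specified estimate or interval rests on none of them. The harm is an inconsistent and incomplete answer to the question in the title, with little effect on error rates.

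**What to change.** Delete the normality pre-test from section VIII and name one analysis per outcome.

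- **Between-arm concentration comparisons:** analyse log concentration, at each time or as AUC, whatever its observed shape, and report the geometric mean ratio with a 90% interval.
- **Pain and opioid summaries:** report one pre-specified difference with a 90% interval. This may be a difference in means with a t-based or bootstrap interval, or a Hodges-Lehmann shift.
- **Any other test:** sensitivity analysis only.
- **Equivalence:** state that it is judged from these intervals.

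The cost is a few sentences and no new data. Two consequences should be accepted openly. A margin on the chosen scale must be stated and justified, which is a separate gap. Precision at 35 per arm may also be limited: with s = 0.472 at CV 50%, the 90% interval runs from the estimate divided by to the estimate multiplied by exp(1.668 × 0.472 × √(2/35)) ≈ 1.21, which leaves little room inside a margin as tight as 0.80-1.25.

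### No baseline adjustment is prespecified: the unadjusted comparison is valid, but a short covariate model would probably narrow the equivalence interval at almost no cost

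*Combined protocol and SAP*

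**What the plan says.** - **Analysis (section VIII).** One paragraph. For continuous outcomes: "Normally distributed data will be assessed using independent sample t-test and non-normally distributed data will be assessed using Mann-Whitney U-test". For equivalence: "Tests for equivalence will be applied for the primary outcome measures", with superiority tests if equivalence fails. Then: "P values <0.05 will be considered statistically significant". No covariate, regression model or stratified analysis appears here or elsewhere.
- **Randomization (section VI.b).** "Participants will be randomized to IV or ESP groups using a computer-generated block randomization sequence". No stratification factor and no allocation ratio are given.
- **Sample size (section V.iii).** "70 adult patients as determined using an online calculator available at" a web address. No margin, SD, power or alpha is stated with it.
- **What is known before treatment (section VI.a).** Age and surgery type come from eligibility: "Any patient >18 years and <81 years undergoing elective cardiac surgery for CABG or valve surgery via sternotomy". BMI must lie between 20 and 50. Sex is noted at screening through the pregnancy check.
- **Prior opioids (section VI.a).** Excluded are those who are "narcotic dependent (opioid intake morphine equivalent > 10 mg/day for more than 3 months". This is a threshold; nothing says that a daily dose is recorded.
- **Dosing (section VI.d).** "Patients will receive lidocaine at a dose of 2 mg/kg ideal body weight (IBW) as bolus divided equally between the two ESP catheters"; the IV bolus is likewise per ideal body weight. The infusion rate in both arms is per kg per hour, with no weight basis stated.

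**The concern.** Equivalence is declared when the confidence interval for the arm difference lies inside the margin. With 70 patients, interval width largely decides whether a verdict is reached, and section VIII moves to superiority testing when it is not. Outcome variation that baseline values could explain stays in the error term under a two-sample test. Chance imbalance between arms in a trial this small is addressed neither by stratification nor in the analysis.

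The characteristics most likely to help are already collected for eligibility or dosing. Body size is the one most specific to this trial: the bolus follows ideal weight, so patients of different actual weight but the same ideal weight receive the same bolus.

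**Working it through.** **1. The plan's figure.** The 70 cannot be reproduced from the documents, because its inputs are missing. Back-solving uses the normal formula for two one-sided tests with a true difference of 0, assuming 35 per arm:

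margin/SD = (z[1−α] + z[1−β/2]) × √(2/n)

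At α = 0.05 per side and 80% power: (1.645 + 1.282) × √(2/35) = 0.70. In reverse, a margin of 0.70 SD gives 35 per arm, or 70. Other inputs also fit 35 per arm: 0.79 SD (α 0.05, 90% power), 0.77 SD (α 0.025, 80%) and 0.86 SD (α 0.025, 90%). The 0.70 SD used below is therefore an assumption.

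**2. Cost and gain of adjustment.** With p baseline covariates and N = 70, the variance of the arm difference relative to the unadjusted one is

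(1 − R²) × (N − 3)/(N − p − 3) = (1 − R²) × 67/(67 − p).

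Break-even R² = p/67:
- p = 2: 3.0%
- p = 3: 4.5%
- p = 4: 6.0%

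**3. Power.** This was simulated with t-based intervals, so the degrees of freedom and chance covariate imbalance are charged. Settings: normal covariates, margin 0.70 SD, 35 per arm, true difference 0, one-sided alpha 0.05, 40,000 trials per cell. Unadjusted power is 78.8%.

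| Covariates | R² 0 | 5% | 10% | 20% | 30% |
|---|---|---|---|---|---|
| 2 | 77.6% | 79.6% | 82.5% | 87.6% | 92.3% |
| 3 | 76.1% | 79.1% | 81.8% | 87.1% | 92.0% |
| 4 | 75.7% | 78.8% | 81.4% | 86.5% | 91.5% |

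**4. Equivalent unadjusted sample size,** 70 ÷ variance ratio:
- R² 10%: 73–76 patients
- R² 20%: 82–85 patients
- R² 30%: 94–97 patients

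Example with p = 3 and R² = 20%: ratio 0.80 × 67/64 = 0.8375, and 70/0.8375 = 83.6.

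**5. Body size and log concentration.** All of the following are assumed: BMI mean 29 and SD 5; actual/ideal weight approximated by BMI/22, so its log has SD 0.157; clearance proportional to actual weight to the power e, with e from 0.5 to 1; total log-SD of concentration 0.3 to 0.5.

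- If the infusion is per ideal weight, share = (e × 0.157)²/(log-SD)². Lowest: (0.5 × 0.157)²/0.5² = 2%. Highest: 0.157²/0.3² = 27%.
- If it is per actual weight, e is replaced by 1 − e. Highest: (0.5 × 0.157)²/0.3² = 7%. At e = 1 the share is 0%.

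Section VI.d does not say which applies, so the range is 0% to about 27%.

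**The case against.** **The unadjusted comparison is not an error.** In a randomized trial it is valid and unbiased, and its interval already allows for chance imbalance. This stands. A reader might infer that the planned analysis is wrong, or that precision is demonstrably lost. The documents support neither: they give no correlation between any covariate and any outcome, and they name no baseline pain score. Below a break-even R² of 3–6%, adjusting would slightly lower power.

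**The equivalence test may not be unadjusted.** Section VIII does not state its form. Reading it as unadjusted is an inference, though a reasonable one, because the only methods named for continuous outcomes are unadjusted.

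**The body-size argument can be pushed too far.** The BMI limits allow a 2.5-fold range of actual weight at one height (50/20), and a reader might take this as the spread to expect. Under the BMI assumptions above, BMI 50 lies (50 − 29)/5 = 4.2 SD above the mean, and patients 1 SD either side of average differ only about 1.4-fold (exp(2 × 0.157)). Most samples are also drawn during the infusion, whose weight basis is unstated.

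**Prior opioid dose is a weak candidate.** Its range is cut by the exclusion, and it may not be recorded as a dose.

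**Larger gaps come first.** The primary outcome, margin, SD and power are not stated, and section VII.iv calls this a pilot study. This limits what can be quantified. It does not remove the point, since one SAP revision can settle all of them.

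**Conclusion.** The point holds as a recommended improvement, not as a defect in validity. The plan prespecifies no covariate adjustment and no stratification, although age, sex, surgery type and body size are available before treatment. It thereby forgoes a likely, but unproven, gain in precision.

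Assuming a 0.70 SD margin, 35 per arm and one-sided alpha 0.05, two to four covariates raise power from about 79% to 81–83%, 87–88% or 92% at R² of 10%, 20% or 30%. If they explain nothing, the cost is 2–4 degrees of freedom and at most about 4 points of power. The upside therefore outweighs the downside, but its size rests on an R² and a margin that the documents do not supply. For log concentration, the contribution of body size could be nil or about a quarter of the variance, depending on the weight basis of the infusion.

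**What to change.** First name the primary outcome and the equivalence margin. Then, before any outcome data are seen, replace the two-sample test for the main comparison by a prespecified linear model:

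- **Pain and morphine equivalents:** arm + age + sex + surgery type (CABG or valve).
- **Log lidocaine concentration:** arm + age + log(actual/ideal weight).

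Fix the analysis scale in advance so that it matches the margin, rather than choosing a transformation after looking at the data; for morphine equivalents, state how zero doses are handled. Take the equivalence interval from the arm coefficient and report the unadjusted result as sensitivity. Use only values fixed before allocation, not intra-operative opioid. Add pre-operative opioid dose to the morphine-equivalent model only if it is recorded as a dose for every patient. State the weight basis of the infusion in section VI.d, so that the role of the body-size covariate is clear.

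Cost: SAP wording and one clarification in the protocol, with no new patients, visits or measurements; 2–3 degrees of freedom, or 4 with opioid dose.
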